#### 3 OBJECTIVES

## 3.1 Primary Objectives

- To compare the OS of subjects with PD-L1 CPS ≥ 20 who are receiving nivolumab combined with ipilimumab to those receiving EXTREME regimen.
- To compare the OS of all study subjects who are receiving nivolumab combined with ipilimumab to those receiving EXTREME regimen

# 3.2 Secondary Objectives

- To compare the OS of subjects with PD-L1 CPS  $\geq$  1 who are receiving nivolumab combined with ipilimumab to those receiving EXTREME regimen
- To evaluate progression-free survival (PFS) based on BICR in all study subjects and those with PD-L1 CPS ≥ 20 who are receiving nivolumab combined with ipilimumab, and those receiving EXTREME regimen.
- To evaluate objective response rate (ORR) based on BICR in all study subjects and those with PD-L1 CPS ≥ 20 who are receiving nivolumab combined with ipilimumab, and those receiving EXTREME regimen.
- To evaluate the duration of response (DOR) based on BICR in all study subjects and those with PD-L1 CPS ≥ 20 who are receiving nivolumab combined with ipilimumab, and those receiving EXTREME regimen.

# 3.3 Exploratory Objectives

- To evaluate OS of subjects with tumor cell PD-L1 < 1% and PD-L1 CPS < 20 who are receiving nivolumab combined with ipilimumab, and those receiving EXTREME regimen.
- To evaluate the OS of subjects with tumor inflammation score measured as gene expression profile (GEP) ≥ 10 who are receiving nivolumab combined with ipilimumab, and those receiving EXTREME regimen.
- To evaluate the OS of subjects with tumor mutation burden (TMB)  $\geq$  7 who are receiving nivolumab combined with ipilimumab, and those receiving EXTREME regimen.
- To evaluate clinical outcomes (OS, PFS, ORR, DOR) by select baseline and on-treatment biomarker expression levels in peripheral blood and tumor biopsy specimens.
- To assess safety and tolerability of nivolumab in combination with ipilimumab and of EXTREME regimen, in all study subjects

- To characterize pharmacokinetics and immunogenicity of nivolumab in combination with ipilimumab as first line therapy in subjects with recurrent or metastatic SCCHN
- To evaluate time to symptom deterioration (TTSD) in each arm as assessed using the Functional Assessment of Cancer Therapy Head and Neck (FACT-H&N) 10-item Symptom Index (FHNSI-10), in subjects with PD-L1 CPS ≥ 20 and also in all study subjects
- To assess the subject's overall health status and health utility using the 3-level version of the EQ-5D (EQ-5D-3L) visual analog scale (VAS) and utility index, respectively, in subjects with PD-L1 CPS ≥ 20 and also in all study subjects
- To assess the subject's cancer-related symptoms and quality of life using components of the FACT-H&N questionnaire, in subjects with PD-L1 CPS ≥ 20 and also in all study subjects.

#### 4 ENDPOINTS

# 4.1 Primary Endpoints

#### 4.1.1 Overall Survival

- OS in randomized subjects with PD-L1 CPS  $\geq$  20
- OS in all randomized subjects

Overall survival (OS) is defined as the time from randomization to the date of death from any cause. For subjects that are alive, their survival time will be censored at the date of last contact date (or "last known alive date"). Overall survival will be censored at the date of randomization for subjects who were randomized but had no follow-up.

OS rate at time T is defined as the probability that a subject is alive at time T following randomization.

Survival follow-up will be conducted every 3 months after subject's off-treatment date.

#### 4.2 Secondary Endpoints

#### 4.2.1 Overall Survival

Overall survival (OS) in randomized subjects with PD-L1 CPS  $\geq$  1 is defined the same way as for the primary endpoints.

## 4.2.2 Progression-Free Survival

Two definitions are used for analysis of Progression-Free Survival (PFS). The primary definition accounts for subsequent therapy by censoring at the last evaluable tumor assessment on or prior to the date of subsequent therapy. The secondary definition is irrespective of subsequent therapy and does not account for subsequent therapy.

Clinical deterioration in the absence of unequivocal evidence of progression (per RECIST v1.1 criteria) is not considered progression for purposes of determining PFS.

PFS rate at time T is defined as the probability that a subject has not progressed and is alive at time T following randomization.

The first on-study tumor assessment is scheduled to be conducted at 6 weeks ( $\pm$  1 week) following randomization. Subsequent tumor assessments are scheduled every 6 weeks ( $\pm$  1 week) up to 12 months, then every 12 weeks until disease progression.

# 4.2.2.1 Primary Definition of Progression-Free Survival (Accounting for Subsequent Therapy)

[figure not shown]
The primary definition of PFS (PFS truncated at subsequent therapy) is defined as the time between the date of randomization and the date of first documented tumor progression, based on BICR assessments (per RECIST v1.1 criteria), or death due to any cause, whichever occurs first. Figure 4.2.2.1-1 show the graphic display of primary definition of PFS.

Subjects who die without a reported progression will be considered to have progressed on the date of their death. The following censoring rules will be applied for the primary definition of PFS:

- Subjects who did not progress or die will be censored on the date of their last evaluable tumor assessment.
- Subjects who did not have any on study tumor assessments and did not die will be censored on their date of randomization.
- Subjects who receive subsequent anti-cancer therapy prior to documented progression will be censored at the date of the last evaluable tumor assessment conducted on or prior to the date of initiation of the subsequent anti-cancer therapy.
- Subjects who did not have a documented progression and received subsequent anti-cancer therapy will be censored at the date of the last evaluable tumor assessment conducted on or prior to the initiation of the subsequent anti-cancer therapy.

Censoring rules for the primary definition of PFS (PFS truncated at subsequent therapy) are presented as follows and in Table 4.2.2.1-1.

Figure 4.2.2.1-1: PFS Primary Definition

**Table 4.2.2.1-1:** Censoring Scheme Used in Primary Definition of PFS

Situation	Date of Progression or Censoring	Outcome
No baseline tumor assessments*	Date of randomization	Censored
No on study tumor assessments and no death*	Date of randomization	Censored
Subsequent anti-cancer therapy started without death or progression per RECIST v1.1 reported prior or on the same day	Date of last evaluable tumor assess- ment prior to or on the date of initi- ation of the subsequent anti-cancer therapy	Censored
Documented progression per RE- CIST v1.1 and no new anti-cancer started before	Date of the first documented pro- gression per RECIST v1.1 (excludes clinical progression)	Progressed
No progression and no death, and no new anti-cancer therapy started	Date of last evaluable tumor assessment	Censored
Death without progression per RE- CIST v1.1 and no new anti-cancer started before	Date of death	Progressed

\* Tumor assessments and death if any, occurring after start of subsequent anti-cancer therapy are not considered.

# 4.2.2.2 Secondary Definition of Progression Free Survival (Irrespective of Subsequent Therapy)

The secondary definition of PFS (ITT definition) is defined as the time between the date of randomization and the date of first documented tumor progression, based on BICR assessments (per RECIST v1.1 criteria), or death due to any cause, whichever occurs first. Figure 4.2.2.2-1 show the graphic display of secondary definition of PFS.

Subjects who die without a reported progression will be considered to have progressed on the date of their death. The following censoring rules will be applied for the secondary definition of PFS:

- Subjects who did not progress or die will be censored on the date of their last evaluable tumor assessment.
- Subjects who did not have any on study tumor assessments and did not die will be censored on their date of randomization.

Censoring rules for the secondary definition of PFS (ITT definition) are presented as follows and in Table 4.2.2.2-1.

Figure 4.2.2.2-1: PFS Secondary Definition

[figure not shown]

Table 4.2.2.2-1: Censoring Scheme for Secondary Definition of PFS

Situation	Date of Progression of Censoring	Outcome
No baseline tumor assessment	Date of randomization	Censored
No on-study tumor assessments and no death	Date of randomization	Censored
Documented progression per RE- CIST v1.1	Date of first documented progression per RECIST v1.1 criteria (excludes clinical progression)	Progressed
No progression and no death	Date of last evaluable tumor assessment	Censored
Death without progression per RE-CIST v1.1	Date of death	Progressed

# 4.2.3 Objective Response Rate

Objective Response Rate (ORR) is defined as the number of randomized subjects who achieve a best response of complete response (CR) or partial response (PR) based on BICR assessments (using RECIST v1.1 criteria) divided by the number of all randomized subjects. Best Overall Response (BOR) is defined as the best response, as determined by the BICR, recorded between the date of randomization and the date of objectively documented progression per RECIST v1.1 criteria or the date of subsequent therapy (including tumor-directed radiotherapy and tumor-directed surgery), whichever occurs first. For subjects without documented progression or subsequent therapy, all available response designations will contribute to the BOR determination. Confirmation of response is required at least 4 weeks after the initial response.

## 4.2.4 Duration of Response

Duration of Response (DOR) is defined as the time between the date of first documented response (CR or PR) to the date of the first documented tumor progression as determined by the BICR (per RECIST v1.1 criteria), or death due to any cause, whichever occurs first. Subjects who start subsequent therapy without a prior reported progression will be censored at the last evaluable tumor assessments prior to initiation of the subsequent anticancer therapy. Subjects who die without a reported prior progression will be considered to have progressed on the date of their death. Subjects who neither progress nor die, DOR will be censored on the date of their last evaluable tumor assessment. DOR will be evaluated for responders (confirmed CR or PR) only.

As a supportive endpoint to DOR, Time to Response (TTR) is usually provided along with DOR and is defined as the time from randomization to the date of the first confirmed documented response (CR or PR), as assessed by the BICR. TTR will be evaluated for responders (confirmed CR or PR) only.

# 4.3 Exploratory Endpoints

Efficacy endpoints (OS, PFS, ORR, DOR) in selected subgroups (based on biomarkers such as PDL1 CPS, PDL1 TPS, GEP and TMB) are defined the same way as described in Section 4.1 and 4.2. Other exploratory endpoints are described as follows.

#### 4.3.1 PFS2

[figure not shown]
Although not specified in the protocol, PFS on next-line therapy (PFS2) is added as an exploratory endpoint to further evaluate the efficacy of the investigational therapy vs the Extreme Regimen.

PFS2 is defined as the time from randomization to objectively documented progression, per investigator assessment, after the next line of therapy or to death from any cause, whichever occurs first. Subjects who were alive and without progression after the next line of therapy will be censored at last known alive date.

The following censoring rules will be applied for PFS2:

- 1. Subjects who did not receive subsequent anti-cancer therapy (i.e. second-line therapy):
  - Subjects who died, the death date is the event date;
  - Else the subject's PFS2 is censored at the last known alive date.
- 2. Subjects who received subsequent anti-cancer therapy (i.e. second-line therapy):
  - Subjects who had a disease progression after the start of subsequent anti-cancer therapy, this disease progression date is the event date;
  - Else if a subject died or started second next line therapy, the date of min (death, start date
    of second next line therapy) is the event date;
  - Else the subject's PFS2 is censored at the last known alive date.

Figure 4.2.2.2: PFS2 Definition

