Tumor Biopsy Sample:	X	
Tumor biopsy specimens will be obtained from consenting participants within all treatment arms at Week 7 and once disease progression has been documented (See Table 5.6-1). Biopsy should be excisional, incisional or core needle (fine needle aspiration is insufficient) and submitted to central lab see also Table 5.6-1

Table 5.1-2: On Treatment Procedural Outline (All Treatments) CA209651 (All Cohorts)

Procedure	During Treatment Visit ^{a,b}	Notes
Saliva Sample: Oral microbiome	X	See Table 5.6-1
Clinical Drug Supplies		
IVRS Drug Vial Assignment	X	
Dispense Study Drug	X	Within 3 days from randomization, the participant must receive the first dose of study medication.

^a For Ipilimumab/Nivolumab Arm: Visits occur every 2 weeks

^b For EXTREME regimen Arm: Visits occur every 3 weeks

Table 5.1-3: Follow-Up Period (all treatment groups)

Procedure	Follow Up, Visits 1 and 2 ^a	Survival Follow-Up Visits ^b	Notes
Safety Assessments			
Targeted Physical Examination	X		To assess for potential late emergent study drug related issues.
Vital Signs	X		
Adverse Events Assessment	X		In survival period only to include toxicities from study therapy.
Review of Concomitant Medication	X	X	Document Subsequent Cancer Therapy
Laboratory Tests	X		CBC w/ differential, LFTs, BUN or serum urea level, creatinine, Ca, Mg, Na, K, Cl, LDH, phosphate, glucose, amylase, lipase. TSH (+ reflex Free T4 and Free T3 collected ONLY if TSH is abnormal). To be done at FU1, to be repeated at FU2, if study related toxicity persists.
Pregnancy Test (WOCBP only)	X		Serum or urine.
Efficacy Assessments			
Tumor Assessment	X	X	Only for participants without progression. - Tumor assessments should occur every 6 weeks (\pm 1 week) for the first 48 weeks, then every 12 weeks (\pm 1 week) until disease progression or treatment is discontinued (whichever occurs later). - CT or MRI of the neck, chest, abdomen, pelvis and all known sites of disease. Use same imaging method as was used at screening/baseline. - MRI of the brain (without AND with Gadolinium contrast) is required for participants with a history of brain metastasis. Note: MRI of the brain is preferred but CT scan is acceptable. Surveillance scans should be performed approximately every 12 weeks, or sooner if clinically indicated. (CT of the head without AND with contrast may be performed if MRI is contraindicated).
Outcomes Research Assessment			
FACT-H&N	X		Can be collected over the phone.

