FHNSI-10		X	Can be collected over the phone.

Table 5.1-3: Follow-Up Period (all treatment groups)

Procedure	Follow Up, Visits 1 and 2 ^a	Survival Follow-Up Visits ^b	Notes
EQ-5D-3L	X	X	Can be collected over the phone.
Health care resource utilization questions	X		To be completed by the site in CRF
Participant Status			
Survival Status	X	X	Every 3 months after FU 2; may be accomplished by visit, phone contact or email, to include assessment of subsequent anti-cancer therapy

^a Follow Up visits 1 (FU1) and 2 (FU2) are in clinic visits. Follow-up visit 1 (FU1) = 30 days from the last dose ± 7 days or coincides with the date of discontinuation (± 7 days) if date of discontinuation is greater than 35 days after last dose, Follow-up visit 2 (FU2) = 90 days (± 7 days) from Follow-up Visit 1

^b Survival Follow Up Visits may be conducted in clinic or via telephone contact: Every 3 Months (± 7 days) from FU2

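### The SAP's PFS2 rule can date an event after the start of a third line, and it relies on next-line progression that the protocol does not schedule anyone to assess

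*SAP*

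**What the plan says.** SAP 4.3.1 states that PFS2 is not in the protocol and adds it as an exploratory endpoint. It is defined as "time from randomization to objectively documented progression, per investigator assessment, after the next line of therapy or to death from any cause, whichever occurs first". The definition adds: "Subjects who were alive and without progression after the next line of therapy will be censored at last known alive date".

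The section then gives rules. Rule 1 covers participants with no subsequent therapy: death is the event, otherwise they are censored at the last known alive date. Rule 2 covers participants with subsequent therapy and has three steps in order:

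1. "Subjects who had a disease progression after the start of subsequent anti-cancer therapy, this disease progression date is the event date".
2. "Else if a subject died or started second next line therapy, the date of min (death, start date"; the line goes on to name the second next line and makes that minimum the event date.
3. "Else the subject's PFS2 is censored at the last known alive date".

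SAP 7.5.11 plans Kaplan-Meier medians and a stratified Cox hazard ratio with a 95% CI. No test is planned.

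On data collection, Protocol Table 5.1-3 restricts follow-up tumor assessment: "Only for participants without progression". Scans run "until disease progression or treatment is discontinued (whichever occurs later". Survival status is collected every 3 months after Follow-Up Visit 2 and "may be accomplished by visit, phone contact or email, to include assessment of subsequent anti-cancer therapy".

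**The concern.** There are two separate problems.

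**Event order.** Step 1 of rule 2 has no upper time limit. If progression on the next line is not recorded, a third line starts, and a later progression is recorded on that third line, the later date is used. The third-line start, which the SAP itself accepts as an event in step 2, is passed over. The definition sentence lists only progression and death, so definition and rules also disagree.

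**Data behind the event.** For someone who progressed before the next line, neither document describes a scan, visit or data item that would capture the next progression. If it goes unrecorded and no third line starts, a participant who dies has PFS2 equal to OS. One who is still alive is counted as progression-free up to a date that a telephone call can set.

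At stake is the meaning of PFS2. An arm difference could reflect how often sites recorded next-line progression rather than disease control on the next line.

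**Working it through.** The documents give no PFS2 median, event count or hazard ratio, so there is no figure to reproduce.

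**Step 1: trace the rule on one hypothetical participant.** The next line starts at month 6, the second next line at month 9, and the first progression recorded after next-line start is at month 13.
- SAP rule 2: step 1 applies, event at month 13.
- Earliest of the three: min(13, 9, death) = month 9.
- Difference: 13 − 9 = 4 months.

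**Step 2: compare with PFS in the same SAP.** SAP 4.2.2.1 censors PFS at the last evaluable tumor assessment. PFS2 censors at the last known alive date. In rule 1 that is sound, because without a next line no progression on it is possible. The issue lies in the final step of rule 2.

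**Step 3: illustrate the size.** Only the 26-month accrual and the 39- and 51-month analysis times come from the documents. The rest are assumptions:
- Exponential times, with median 5 months to first progression.
- 60% start a next line 0.7 month later; median 4 months to progression on it.
- 50% of those start a second next line 1 month after that progression, if alive; median 2.5 months to the following progression.
- Median 5 months from progression to death: from next-line progression for those with a next line, otherwise from first progression.
- q is the share of progressions after next-line start that are recorded.

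There were 200,000 simulated participants per scenario. The SAP's third-line-start event is kept. Median PFS2 in months at the 51-month cut-off:

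| q | True | SAP rule | Excess | Earliest of three |
|---|---|---|---|---|
| 0 | 11.81 | 14.09 | 2.28 | 14.09 |
| 0.3 | 11.78 | 13.49 | 1.71 | 13.38 |
| 0.6 | 11.78 | 12.80 | 1.02 | 12.67 |
| 1 | 11.76 | 11.76 | 0 | 11.76 |

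- **Reordering alone** recovers 13.49 − 13.38 = 0.11 and 12.80 − 12.67 = 0.13 month. If 10% of next-line participants change line before progressing, it recovers up to 12.60 − 12.32 = 0.28.
- **Override frequency** at q = 0.3 and 0.6 is 3.4% and 4.0% of participants (2.9% and 3.3% at 39 months). It reaches 8.0% with 10% early line changes.
- **Progressed but censored as alive**, for q from 0.6 to 0: 1.0% to 2.5% at 51 months, 2.3% to 5.8% at 39 months.
- **Other line shares** (40% to 70% reaching a next line, 30% to 60% of those a third) at q = 0.3: excess from 12.87 − 11.90 = 0.97 to 14.23 − 11.68 = 2.55 months.

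**Step 4: hazard ratio.** With a true ratio of 1 and 4,000 participants per arm, recording of 30% in arm A and 60% in arm B gave 0.925. The reverse gave 1.063. Equal recording of 30% gave 0.99.

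**Step 5: a second set of assumptions.** First-line PFS median 5.0 months; 25% never reach a next line and die at first progression; next-line PFS median 3 months; survival after second progression median 4 to 6 months. The true median is 8.4.
- With 30% to 50% starting a third line, the SAP rule gives 9.6 to 10.2 with half recorded (excess 1.2 to 1.8) and 10.8 to 12.6 with none recorded (excess 2.4 to 4.2).
- With the third-line event switched off, the figures are 10.4 to 11.0 and 12.8 to 14.6.
- Also with it off, moving the censoring date of living participants back to next-line start changes these only to 10.4 to 10.9 and 12.7 to 14.2.

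**The case against.** The strongest reply is that the SAP already has a safeguard. Step 2 of rule 2 makes the start of a second next line an event, and follow-up records subsequent therapy throughout. That stands. A reader might infer that every unrecorded progression turns PFS2 into OS; this holds only where no third line starts, and Step 5 shows how far ignoring the safeguard inflates the excess.

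It can also be said that the schedule is fuller than 3-monthly calls. Follow-Up Visits 1 and 2 are in-clinic visits, about 30 days after last dose and 90 days after that, with a targeted physical examination and review of subsequent therapy. Participants who stop treatment without progression continue to be scanned until they progress (Protocol 3.1, Follow-up Phase), so progression after an early next line can be captured. PFS2 is investigator-assessed, so locally observed progression can count, and the case report form, which is not in the documents, may collect it. All of this narrows the gap to participants who progressed first. It does not close it, because neither document says how their next-line progression is recorded. The PFS2 figure is not reproduced in the text available, so whether it clarifies event order cannot be seen.

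A reader might also infer that PFS2 is necessarily overstated, or that it favours one arm. The documents support neither. With complete recording there is no excess apart from the event-order issue. A third line started for reasons other than progression ends PFS2 early. No passage indicates that recording differs by arm.

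**Conclusion.** The concern holds in a limited form. Rule 2 can give a later date than an event the SAP itself recognises, and the definition sentence and the rules disagree; both follow from the text alone. The drift toward OS is conditional on incomplete recording of next-line progression among participants who progressed before the next line and did not start a third.

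The size rests wholly on assumptions: about 1.0 to 2.3 months on the median in the base illustration for 60% down to 0% recorded, none at 100%, and different values under other inputs. Most of the excess comes from unrecorded progression; event order contributes about 0.1 month, up to 0.3. The direction of any hazard ratio bias is unknown.

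Severity is minor. PFS2 is exploratory, has no test and lies outside the testing hierarchy in SAP Appendix 4. A reader who took this as a threat to the OS conclusions would be going beyond the documents.

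**What to change.** 1. For participants with a next line, define the PFS2 event as the earliest of documented progression after next-line start, start of second next-line therapy, and death. Amend the definition sentence to match.
2. Tabulate by arm the source of each PFS2 event (progression, second-next-line start, death) and the number of next-line participants with any disease evaluation after next-line start. Since reordering leaves most of the possible excess in place, this table tells the reader how far to trust the estimate.
3. Report time to second subsequent therapy or death as a supportive analysis. Survival follow-up already collects what it needs.
4. Add a sensitivity analysis that censors rule 2 participants at their last disease evaluation on or after next-line start, or at next-line start if there is none. Keep it as a sensitivity analysis: it censors living participants early while still counting deaths, and in the check above a similar change barely moved the median.

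The cost is SAP wording, programming and one extra table. No new data collection is required and no OS analysis changes.
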